5.2.2 Analyses for Categorical Data

Categorical data will be summarized by presenting the number of subjects and the percentage.

The Wilcoxon rank sum statistic will be used to assess the randomized arm difference in the distribution (median) of the number of hypoglycemic events per subject.

The Wilcoxon rank sum statistic will be used to assess the randomized arm difference in the distribution (median) of the number of thrombocytopenia events per subject.

The Wilcoxon rank sum statistic will be used to assess the randomized arm difference in the distribution (median) of the number of hypertriglyceridemia events per subject.

Hypoglycemic risk ratio, thrombocytopenia risk ratio, and hypertriglyceridemia risk ratio may be estimated by analysis methods based on a counting process approach (Andersen and Gill, 1982) for analyzing recurrent events (using the robust sandwich estimate of the covariance matrix by Lin and Wei (1989) in order to take into account the non-independence of multiple events for a single subject).

5.3 Methods to Manage Missing Data

For the analysis of safety endpoints, the sponsor data standard rules for imputation will be applied.

CCI

CCI

Pharmacodynamic parameters

- Missing data for all the pharmacodynamic parameters will be treated as such and no imputed values will be derived when presenting descriptive statistics at scheduled assessments.
- Concentrations below Lower Limit of Quantification (LLQ) will be set to half-LLQ (ie LLQ/2) for summary outputs; in listings BLQ values will be reported as “<LLQ”. Derived data by calculation (eg indirect bilirubin, choriogonadotropin Beta) will not follow the rule described above and will be reported as it is (ie reported as “< LLQ” in listing and missing if summary statistics are required).
- Derived data by calculation CCI will not follow the rule described above and will be reported as <LLQ (in listings) with a derived value of (<negative value> minus 0.0001 = positive value) when generating summary statistics, as required.
- Any values above the Upper Limit of Quantification (ULQ) will be assigned to the ULQ for display purposes in Figures and for computation of summary statistics; in listings ULQ values will be reported as “>ULQ”.
- Observed cases will be used when analyzing continuous variables using Mixed-Model Repeated Measures (MMRM)[1], analysis of covariance (ANCOVA) and nonlinear models.

6 ANALYSES AND SUMMARIES

6.1 Primary Endpoint

Primary endpoint will be analyzed on the FAS and PPAS. These analyses will be based on observed cases.

6.1.1 Primary Analysis on % Liver Fat assessed using MRI-PDF

Population: Entire Study Population

Endpoint: Relative change from baseline

Parameters: % Liver fat assessed with MRI-PDFP:

- Analysis time points: **all** applicable **post** Day 1/Visit 5 time points where **scheduled** assessment of specific continuous parameter is outlined in protocol
- Analysis population: FAS and PPAS (as sensitivity analysis).
- Analysis methodology: Log transformed relative change from baseline will be analyzed using MMRM model with log(baseline) as a covariate (specified in section 5.2.1.2).

Reporting results:

- Raw data and percent changes from baseline: Randomized subject, number of subject contributing to summary, sample size, mean, standard deviation, median, minimum, maximum, Q1 and Q3 at baseline and post-baseline visits will be presented for each randomized arm (see Appendix 2 for further detail).
- MMRM Outputs:
 - ✓ Adjusted geometric LS mean estimates with 80% confidence interval for each randomized arm along with the translation in percent change over time,
 - ✓ Ratio of adjusted geometric LS mean estimates for each active randomized arm against placebo and the corresponding 80% confidence interval along with the translation in percent difference over time.

Figures from MMRM outputs:

1. Line plot of percent change from baseline after back transformation of adjusted geometric LS means with 80% confidence interval over time (see Appendix 3.3),
2. Line plot of percent change from baseline placebo-adjusted after back transformation of adjusted geometric LS means ratios with 80% confidence interval over time (see Appendix 3.4),
3. Percent change from baseline after back transformation of adjusted geometric LS means with 80% confidence interval at Week 16 (see Appendix 3.5),
4. Percent change from baseline placebo-adjusted after back transformation of adjusted geometric LS means ratios with 80% confidence at Week 16 (see Appendix 3.6).

Note regarding the figures:

Instead of producing 4 independent figures, and in order to having a better understanding of the placebo effect, 1 figure containing side-by-side two panels presenting bullet 1 and 2 outputs (right panel for response over time and left panel for placebo adjusted response over time), and 1 figure with two panels presenting side-by-side bullet 3 and 4 outputs (right panel for response at Week 16 and left panel for placebo adjusted response at Week 16) should be produced.

Note regarding MRI windowing:

Subjects with MRI assessment up to a maximum of 48Hrs post last dose on Week 16 instead of 24Hrs post last dose on Week 16 as currently stated will be included in FAS and PPAS. This is to permit assessment of the primary endpoint while on drug.

6.1.2 Supportive Analyses on % Liver Fat Assessed using MRI-PDFF

6.1.2.1 Dose-Response Model

For % Liver Fat assessed by MRI-PDFF at Week 16, the analysis will be performed on the FAS without covariates in subject with nonalcoholic fatty liver disease (entire study population). The primary endpoint is the log transformed relative change from baseline in liver fat at Week 16 using the dose response model as described in section 5.2.1.3.

Endpoint: Relative change from baseline

Parameter: % Liver fat assessed by MRI-PDFF

- Analysis time points Week 16
- Analysis population: FAS in subject with nonalcoholic fatty liver disease (entire study population)
- Analysis methodology: Natural log-transformed relative change from baseline in % liver fat will be analyzed using the Dose-Response model (specified in section 5.2.1.3).
- Supporting objective: Primary Objective

Reporting results for model:

- The three parameters of the Emax model (E0, ED50, and Emax) along with their respective 80% confidence interval if non-linear model. .

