2.1 Study Objectives

Primary Objective:

 To evaluate the dose-response for the effect on liver fat, as assessed via MRI-PDFF, with a range of PF-05221304 doses administered daily in adults with nonalcoholic fatty liver disease (entire study population)
Secondary Objective(s):

 To evaluate the dose-response for the effect on ALT with a range of PF-05221304 doses administered daily in the 1st tier stratification comprising of adults with diagnosed/presumed nonalcoholic steatohepatitis, only To evaluate the safety and tolerability of a range of PF-05221304 doses administered daily in adults with nonalcoholic fatty liver disease (entire study population)
Tertiary Objective(s):

 To evaluate the dose-response for the effect on liver fat, over time, with a range of PF-05221304 doses administered daily in adults with nonalcoholic fatty liver disease (entire study population)

CCI	
	
 To evaluate the dose-response for the effect on key liver function tests and NASH-related biomarkers over time, with a range of PF-05221304 doses administered daily in the 1st tier stratification comprising of adults with diagnosed/presumed nonalcoholic steatohepatitis, only
CCI	
	
 To evaluate the dose-response for the effect on other potentially mechanism-related parameters and metabolic parameters, over time, with a range of PF-05221304 doses administered daily in adults with nonalcoholic fatty liver disease (entire study population)
	
 To evaluate the dose-response for the effect on glycemic parameters, over time, with a range of PF-05221304 doses administered daily in the 2nd tier stratification comprising of adults with T2DM, only
CCI	

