5.2.1.2 Longitudinal Analysis

The over time effect of PF-05221304 on primary, secondary, and tertiary endpoints (see list in section 3) will be analyzed using the MMRM approach with randomized arm, time and randomized arm by-time interaction as fixed effects, subject as random effect using unstructured (UN) covariance structure. Baseline (in raw scale or log scale depending on the endpoint) will be included as covariate in the model.

Other covariance structures (eg Compound Symmetry (CS), Autoregressive(1) [AR(1)], Heterogeneous CS (CSH), and Heterogeneous AR(1) [ARH(1)]) will be considered if convergence in the previous model is not met.

The effect of PF-05221304 doses at all **post-randomization** visits will be estimated by the least-square (LS) means as well as LS mean differences against placebo respectively from the model described above.

For all analyses performed on log-transformed relative change from baseline (RCBL), the LS mean estimates and their corresponding confidence intervals (CIs) will be obtained for each randomized arm and week. Differences (and corresponding confidence intervals) between LS mean estimates will be obtained comparing randomized arms for each week. All LS means and LS mean differences (including CI's) will be back transformed to provide adjusted geometric LS means and ratios of adjusted geometric LS means. Then, percent change from baseline will be calculated as follows:

$$\text{Percent change} = 100 * (\text{RCBL} - 1)$$

where RCBL is either the adjusted geometric LS means estimate or the ratio of adjusted geometric means coming from the statistical model. The corresponding 80% CIs will be calculated as well.

For all analyses performed on raw scale, the LS means estimates and their corresponding confidence intervals (CIs) will be obtained for each randomized arm and week. Differences (and corresponding confidence intervals) between LS means will be obtained comparing randomized arms for each week.

Regardless if the data are analyzed in raw scale or after log-transformation, the inter- and intra-subject variability from the statistical model will be available and reported.

For % liver fat assessed by MRI-PDFP analyzed on log-scale, 80% confidence intervals will be presented for the LS geometric mean ratio.

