5.2.1.3 Supportive Efficacy Analyses

The effect of PF-05221304 doses on % Liver Fat assessed with MRI-PDF **CCI** will be performed **post-database release** using the following dose-response model on the individual natural log transformed of relative change from baseline observed at Week 16.

Non-linear Dose-Response Model

The 3 parameter Emax model will be fit to the response at Week 16 on all doses. If the model converges, model estimated parameters will be presented along with their standard error (SE), 80% (Liver Fat **CCI**) confidence intervals as well as p-values (one-sided). The model projected placebo adjusted treatment effect for each PF-05221304 dose will also be presented along with their SE and confidence intervals. The Delta-Method will be employed to estimate standard errors and confidence intervals.

If the model fails to converge, the message “Algorithm fails to converge” will be displayed.

The 3-parameter Emax model is expressed as follows:

$$y_{ij} = E_0 + E_{\max} \frac{d_i}{d_i + ED_{50}} + \varepsilon_{ij}$$

, where y_{ij} denotes the response for subject j on dose i , d_i denotes dose i , and $\varepsilon_{ij} \sim \text{i.i.d } N(0, \sigma^2)$.

Alternative Dose-Response Model in case of no convergence

Selection of alternative dose-response model (eg linear, quadratic) may be explored after visual inspection of the response at Week 16. The rationale of the model selection and the subsequent analyses may be included in the CSR.

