5.2.1.4 Covariate Interaction

The impact of the covariates will be examined to identify potential parameters that could influence the primary endpoint (ie % liver fat using MRI-PDFF).

CCI

For the categorical covariate, an ANCOVA model which includes the randomized arm, covariate and the randomized arm-by-covariate interaction as independent factors, and log(baseline) value as an additional covariate will be used. If the p -value for the interaction is less than 0.05, the LS means and LS mean differences will be displayed by each level (absence = 0 or presence = 1) of the categorical covariate.

For the continuous variable (eg weight, baseline), an ANCOVA model which includes the randomized arm, covariate and the randomized arm-by-covariate interaction as independent variables, and log(baseline) value as an additional covariate will be used. If the p -value for the interaction is less than 0.05, the LS means and LS mean differences will be displayed at Q1, median, and Q3 levels of the continuous covariate.

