9 APPENDICES

Appendix 1. SUMMARY OF EFFICACY ANALYSES

Endpoint	Analysis Set	Statistical Method	Model/ Covariates/ Strata	Missing Data	Interpretation
Percent change from Baseline in % Liver Fat assessed by MRI-PDFD Over Time	FAS and PPAS	MMRM on log-transformed relative change	Treatment, time and treatment-by-week interaction as fixed effects, subject as random effect with log(baseline) as covariate.	No Imputation	Primary Analysis
Percent Change from Baseline in % Liver Fat assessed by MRI-PDFD at Week 16	FAS and PPAS	ANCOVA on log-transformed relative change	Treatment, Weight and treatment-by-Weight interaction as fixed effects, subject as random effect with log(baseline) as additional covariate.	No Imputation	Sensitivity analysis with two covariates on primary endpoint.
Percent Change from Baseline in % Liver Fat assessed by MRI-PDFD at Week 16	FAS and PPAS	ANCOVA on log-transformed relative change	Treatment, concomitant drug and treatment-by-concomitant drug interaction as fixed effects, subject as random effect with log(baseline) as additional covariate.	No Imputation	Sensitivity analysis with two covariates on primary endpoint.
Percent Change from Baseline in % Liver Fat assessed by MRI-PDFD at Week 16	FAS	Dose-Response model	See section 5.2.1.3	No Imputation	Supportive analysis on primary endpoint
Percent change from Baseline in ALT Over Time	FAS	MMRM on log-transformed relative change	Treatment, time and treatment-by-week interaction as fixed effects, subject as random effect with log(baseline) as covariate.	No Imputation	Secondary analysis

Endpoint	Analysis Set	Statistical Method	Model/ Covariates/ Strata	Missing Data	Interpretation
Percent Change from Baseline in ALT at Week 16	FAS	Dose-Response model	See section 5.2.1.3	No Imputation	Supportive Analysis on secondary endpoint
Tertiary endpoints: Change from Baseline over time	FAS	MMRM on change from baseline	Treatment, time and treatment-by-week interaction as fixed effects, subject as random effect and baseline as covariate	No Imputation	Tertiary analysis
Tertiary endpoints: Percent change from Baseline over time other than % Liver Fat using MRI-PDF	FAS	MMRM on log-transformed relative change	Treatment, time and treatment-by-week interaction as fixed effects, subject as random effect and log(baseline) as covariate.	No Imputation	Tertiary Analysis

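### The Week 16 liver-fat Emax model leaves out log(baseline), and the primary MMRM leaves out the 1st-tier stratum; the cost is precision, not bias

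*SAP*

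**What the plan says.** The primary objective in SAP 2.1 is a dose-response objective: "To evaluate the dose-response for the effect on liver fat, as assessed via MRI-PDFF". SAP 5.2.1.3 gives the one fully specified dose-response model: "The 3 parameter Emax model will be fit to the response at Week 16 on all doses". Its equation has dose as the only regressor. SAP 6.1.2.1 applies it to log relative change in liver fat, states that "the analysis will be performed on the FAS without covariates", and tags it "Supporting objective: Primary Objective". Appendix 1 of the SAP labels the fit supportive.

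The other models of this response adjust for baseline:

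- Primary MMRM, SAP 6.1.1: "Log transformed relative change from baseline will be analyzed using MMRM model with log(baseline) as a covariate".
- General MMRM method, SAP 5.2.1.2: "Baseline (in raw scale or log scale depending on the endpoint) will be included as covariate in the model".
- Week 16 ANCOVAs, SAP 5.2.1.4: "log(baseline) value as an additional covariate will be used".

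For the strata, Protocol 4.3 sets up a two-tier stratification and aims to balance the arms within the 1st tier (diagnosed/presumed NASH versus NAFLD with likely minimal inflammation and fibrosis). SAP 4.5 gives rules for subjects randomised in the wrong stratum. Yet Appendix 1 specifies the primary MMRM as "Treatment, time and treatment-by-week interaction as fixed effects, subject as random effect with log(baseline) as covariate", in a column whose heading includes strata. Protocol 9.2.1, SAP 5.2.1.2 and SAP 6.1.1 name no stratum either. SAP 6.4 refers to analyses by stratum, which are separate analyses. Neither document gives a reason for either omission.

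**The concern.** Using log relative change as the response does not fully account for baseline. It fixes the slope of log Week 16 on log baseline at 1. If the true slope differs, some variance that log(baseline) would explain stays in the residual and passes into the standard errors of E0, Emax, ED50 and each placebo-adjusted dose effect. These are the outputs that speak most directly to the primary objective.

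There is also a matter of consistency. The reader will have two sets of Week 16 dose effects on the same response, one baseline-adjusted and one not. The figure template in SAP Appendix 3.5, still to be adapted for this study, overlays the two.

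For the MMRM, a factor that the randomisation balances but the model omits makes the model-based standard errors too large whenever that factor is prognostic beyond log(baseline).

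**Working it through.** **The plan's own figure.** The documents state no precision for the Emax fit. The only related figure is power of at least 80% for a 30% placebo-adjusted difference at 60 completers per arm (Protocol 9.1). Taking 30 and the stated SDs literally in the same units, power at one-sided 10% exceeds 0.99 at both 60 and 30 per arm, so the bound is met. This point does not rest on that figure.

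**Part 1: log(baseline) in the Emax model**

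Let rho be the within-arm correlation of log baseline with log Week 16 liver fat, and k the ratio of the Week 16 SD to the baseline SD on the log scale. In units of the baseline variance:

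- residual variance of log(Week 16/baseline), no covariate: k² + 1 − 2·rho·k
- residual variance after regression on log(baseline): k²(1 − rho²)
- interval width with the covariate, relative to without: sqrt[k²(1 − rho²)/(k² + 1 − 2·rho·k)]

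The ratio is 1 when rho·k = 1, that is, when the log-log slope is 1.

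The documents give neither input on the log scale. Treating the SDs in Protocol 9.1 as variance components gives rho = 7.8²/(7.8² + 6.2²) = 60.84/99.28 = 0.613. Their scale is not stated, so this is illustrative. The values 0.5 and 0.8 are assumed, as is k.

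| k | rho 0.5 | rho 0.613 | rho 0.8 |
|---|---|---|---|
| 1 | 0.866 | 0.898 | 0.949 |
| 1.2 | 0.933 | 0.963 | 0.9985 |
| 1.3 | 0.955 | 0.981 | 0.999 |
| 1/rho | 1.000 | 1.000 | 1.000 |

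For example, at k = 1 and rho = 0.613 the variance ratio is (1 − 0.376)/(2 − 1.226) = 0.806, whose square root is 0.898. The unadjusted interval is then 1/0.898, about 11%, wider, and 60 completers per arm unadjusted are worth about 60 × 0.806 = 48 adjusted.

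Simulated Emax fits agree. The settings were doses 0, 2, 10, 25 and 50 mg, 60 per arm, baseline log SD 0.5, Emax = log(0.4), ED50 of 3 or 8 mg, delta-method 80% intervals and 600 trials per setting. For rho 0.5/0.613/0.8, mean width ratios were:

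- k = 1: 0.867–0.873, 0.899–0.904, 0.949–0.953
- k = 1.2: 0.931–0.937, 0.964–0.966, 1.000
- k = 1/rho: 1.000–1.003 across settings
- k rising with dose (1, 1.05, 1.2, 1.3, 1.3), rho 0.613: 0.958–0.961, a gain of about 4%

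**Bias.** A separate simulation used log SD 0.55, ED50 6 mg, a maximum effect of −55% and rho 0.613. Bias in the dose effects was at most 0.01 log units for both fits with complete data, with dropout of 1/6 at random, and with baseline-dependent dropout that was the same in all arms. Only when dropout depended on baseline in opposite directions on placebo and active did the unadjusted fit shift, by 0.06 to 0.08 log units (at 50 mg, −54% against a true −51%). The adjusted fit stayed within 0.01.

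**Part 2: 1st-tier stratum in the MMRM**

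Let R² be the share of residual variance the stratum explains beyond log(baseline) (assumed). The width ratio is approximately sqrt(1 − R²): sqrt(0.95) = 0.975 and sqrt(0.90) = 0.949. Simulation used 4,000 Week 16 ANCOVAs in place of the MMRM, with 60 per arm split 30/30 and log(baseline) in both models:

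| Added terms | R² 0 | R² 0.05 | R² 0.10 |
|---|---|---|---|
| 1st tier | +0.01% | −2.56% | −5.21% |
| 1st tier plus a non-prognostic T2DM term (40% prevalence assumed) | +0.18% | −2.38% | −5.04% |

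Omitting a balanced prognostic stratum also makes the test conservative. The true one-sided level is 1 − Φ(1.2816/sqrt(1 − R²)): 0.099 at R² = 0.01 and 0.088 at R² = 0.10, instead of 0.10.

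**The case against.** The strongest reply is that nothing here is an error. The covariate-free Emax fit is an explicit, pre-specified choice for a supportive analysis. The decision rule in SAP 5.1 concerns each dose against placebo, and the MMRM for that comparison already adjusts for log(baseline). That is right, and it limits part 1 to the dose-response outputs.

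The sizes are also assumed. The 13% figure needs rho = 0.5 with k = 1; the gain is about 4% if k rises with dose as above, and nil at slope 1. The 8% liver-fat entry floor makes k of 1 or more likelier by restricting baseline spread, but it applies at Screen 2, while the analysis baseline is a later MRI. It therefore does not settle k. The 0 to 13% range covers the cases examined and is not a bound.

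The overlay argument is weak on its own: Appendix 3.5 is a borrowed template, and adjusted and unadjusted dose effects estimate essentially the same thing under randomisation.

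The stratum part is the less certain half. Without a biopsy, the 1st tier is defined by ALT and liver stiffness, and nothing in the documents shows that it predicts relative change in liver fat beyond baseline. The list of interaction covariates in SAP 5.2.1.4 is partly redacted and may include strata, but that would not put them in the primary MMRM.

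These points reduce the weight of the concern. They give no reason to leave out a baseline value already collected, or the factor on which randomisation is balanced.

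**Conclusion.** The concern holds, as a matter of precision and consistency. The SAP treats one Week 16 model of log relative change differently from the others without explanation, and its primary MMRM omits the 1st-tier stratum.

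The likely cost is 0 to 13% of Emax interval width, depending on an unknown log-log slope, and 0 to about 5% of MMRM interval width, depending on an unknown stratum R². No gain in power is claimed. The absence of bias assumes that dropout does not depend on baseline differently by arm; it took an extreme pattern to move the top-dose estimate by about 3 percentage points. The sponsor should make the change, and part 1 alone justifies it.

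**What to change.** - **Emax model (SAP 5.2.1.3 and 6.1.2.1).** Add centred log(baseline) as a linear term on E0, and likewise in any linear or quadratic fallback. If the curve is overlaid on the LS means, plot it at mean log(baseline). Keep the covariate-free fit as a sensitivity analysis. Appendix 1 also sends the ALT dose-response model to 5.2.1.3, so state whether the change applies there; no ALT gain was assessed.
- **MMRM (SAP 5.2.1.2 and Appendix 1).** Add the 1st-tier stratum as a fixed effect in entire-population models, with T2DM status as an optional further covariate. Use the stratum as corrected under SAP 4.5, which for misassigned subjects differs from the one used at randomisation, and say so. Omit whichever tier is constant in NASH-only or T2DM-only models.
- **Timing and governance.** Make the change before unblinding. Record whether the MMRM change counts as a major modification of the primary analysis, which under Protocol 9 and SAP 2 would require a protocol amendment. The SAP has already added baseline to the MMRM in Protocol 9.2.1 while protocol Amendment 2 remained effective. That suggests, without proving, that covariates can be handled in the SAP.

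The cost is SAP wording and one to three degrees of freedom out of about 300 completers, with no new data. If the terms are not prognostic, the simulated change in interval width is at most about +0.3% (Emax with log(baseline)), +0.01% (1st tier) or +0.18% (both tiers).
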